### 5.3 Grading of Adverse Events

Adverse events (toxicities) will be graded according to the NIH's Common Terminology Criteria for Adverse Events v4.0 (CTCAE):

Grade 1 Mild AE

Grade 2 Moderate AE

Grade 3 Severe AE

Grade 4 Life-threatening or disabling AE

Grade 5 Death related to AE

Any life-threatening toxicity (Grades 4 and 5) should be reported immediately (within 24 hours) to the PI and to the Data Safety Monitoring Board.

## 6.0 DOSE MODIFICATIONS FOR ADVERSE EVENTS

**The Study Chair must be notified of any dosage modification.**

### 6.1 Dose Modifications for Potential Propranolol Specific Side Effects

#### 6.1.1 Hypotension and Bradycardia

**Baseline blood pressure (BP)** is defined as the blood pressure obtained at the examination used for study enrollment. This baseline BP should be obtained as follows: 1) Obtain 3 serial blood pressures from the same extremity with the patient in the same position that are separated by at least 5 minutes. Avoid using the lower extremity if possible. BP will not be obtained from the affected limb. 2) Average the systolic blood pressure from the 2nd and 3rd measurements. 3) Average the diastolic blood pressure from the 2nd and 3rd measurements. 4) The baseline BP is the average of the systolic over the average of the diastolic measurements.

Heart rate will be measured by palpation of the radial pulse serially from the same extremity for 15 secs, separated by at least 5 minutes. In the case of extremity LMs, pulse rate will not be obtained from the affected limb. 2) Average the pulse rate from 2nd and 3rd measurements.

6.1.1.1 Patient must have no evidence of clinical contraindications with normal HR and BP parameters prior to dose escalation occurring. If individuals are found to have a fall in their blood pressure or heart rate to below normal limits, but asymptomatic:

- a. patient will be not have dose escalation
- b. patient will be evaluated for dose escalation at the next 2-week cycle.
- c. if HR and BP fall below normal ranges and patient is symptomatic, propranolol will be held for 2 weeks, and re-introduced at the next visit at the lowest tolerated dose.
- d. if patient is at the lowest dose already (0.5mg/kg/day), they will be pulled from the study and re-evaluated at the next visit.
- e. Patients receiving 0.5mg/kg/day who experience HR or BP decrease below the normal range at 4 weeks must be taken off protocol therapy.

Table 5. Side effects and propranolol dosing guidelines

Hypotension and Bradycardia	Propanolol Dosing Guidelines
Within normative range	No change in dose
Below normal range, asymptomatic	Cardiology evaluation, EKG, echocardiogram; if cardiac status is acceptable, patient will not have dose escalation and remain at current dose level with subsequent re-evaluation at 2 weeks
Below normal range, symptomatic	Discontinue propranolol (off protocol therapy. Re-evaluate after 2 weeks. If HR and BP then fall within normal parameters they will be reintroduced to the study with dose de-escalation to the prior tolerated dose of propranolol. If HR/BP below normative range at 0.5mg/kg/day, patient will be removed from study)

Hypoglycemia	Management/Next Dose for propranolol
Blood glucose >80 mg/dl	No change in dose
Blood glucose <80, >60, asymptomatic	Clinical evaluation, review feeding schedule, repeat test after more

Hypoglycemia	Management/Next Dose for propranolol
	frequent/supplemental feeds
Blood glucose <80, symptomatic	Discontinue propranolol (off protocol therapy)

Bronchospasm	Management/Next Dose for propranolol
Transient/self-limited episode	Clinical evaluation, may continue at same dose
Associated with URI	Hold propranolol till URI resolves; if >7 days, off protocol
Not associated with URI, persistent or requiring new medical treatment	Discontinue propranolol (off protocol therapy)

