Propranolol has been used for different indications for many years. Most recently, propranolol gained FDA approval for use in infants with hemangiomas, a related vascular anomaly (Hemangeol ®) (<http://www.accessdata.fda.gov/scripts/cder/drugsatfda/index.cfm?fuseaction=Search.DrugDetails>, accessed May 23, 2014). FDA-approved dose range for treating hemangiomas in infants (>5 weeks old, >2kg) ranged from 1-3mg/kg/day in divided doses. Propranolol has also been used to treat pediatric supraventricular tachycardia at doses up to 4mg/kg/day[3, 4]. However,  $\beta$ AR antagonists are not without potential adverse effects, including hypotension, bradycardia, hypoglycemia, bronchospasms, and sleep disturbances[5].

The dose range of 0.7-1mg/kg/day was chosen for our LM patients as it was the low end of dose range for infants treated with propranolol for problematic hemangiomas. At this dose, no significant hemodynamic adverse effects were noted in our LM patients. However, when patients stopped propranolol or their dose fell below 0.7mg/kg/day, they suffered rebound worsening of their symptoms. Moreover, inflammatory events such as infections temporarily overcame the effects of 0.7-1mg/kg/day of propranolol. Thus, it is unknown whether we have achieved maximum propranolol efficacy at our current dose range. We propose to escalate propranolol dosages up to 3mg/kg/day in this study, still well below the dose ranges currently used in clinical settings.

In this clinical trial, we will examine whether QMR can quickly and accurately quantify lymphedema severity, as well as evaluating whether we have optimized propranolol usage for treatment of LM patients. The primary endpoints for this study are to: 1) validate QMR as a tool for evaluation of lymphedema, and 2) ascertain whether LM patients can tolerate higher doses of propranolol, as measured by known propranolol adverse effects and patient-reported symptoms. A secondary endpoint will address whether patient-reported LM symptoms and quality of life are improved with higher doses of propranolol; objective findings such as LM size on physical examination and imaging studies will be analyzed as well. In addition, LM tissue biopsies will be acquired from patients before and after propranolol treatment for further analyses of disease progression.

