## EXPERIMENTAL DESIGN SCHEMA

The dose escalation for each patient will be as follows (Table 1):

Table 1. Propranolol intra-patient dose escalation schedule and assessments

	Propranolol Dose Schedule*	Assessments		
		Subjective	Objective	Other
Week 1 (initiation)	0.5 mg/kg/day, divided bid	Entrance Interview, Quality of Life Questionnaire	Physical Exam, Imaging	Blood Draw, a Tissue Biopsy a
Week 2	1 mg/kg/day, divided bid a,b	Quality of Life Questionnaire	Physical Exam	
Week 4	2 mg/kg/day, divided bid a,b	Quality of Life Questionnaire	Physical Exam	Blood Draw
Week 6	3 mg/kg/day, divided bid a,b	Quality of Life Questionnaire	Physical Exam	
Week 8	3 mg/kg/day, divided bid a,b	Exit Interview, Quality of Life Questionnaire	Physical Exam, Imaging	Blood Draw, a Tissue Biopsy a

\*Weight will be rounded to the nearest 10-kg increment

aDose escalation in the absence of clinical contraindications.

bIn the presence of clinical contra-indications, the patients will remain on their current level of dosage, or decreased to the previous level, or have their medications held.

A maximum of 8-weeks of therapy may be administered.

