### 2.3.2 Risk Assessment

#### 2.3.2.1 Hypotension and Bradycardia:

Studies have shown that the peak effect of oral propranolol on blood pressure and heart rate occurs 1 to 3 hours after it is taken[28, 29]. As such, current recommendations are that patients should have HR and BP done at baseline and also hourly for the first 2 hours after a dose increase, and at least once after the target dose is achieved. As dose response is generally most significant after the first dose, once normal vitals are obtained with the first dose there is no recommendation that vitals should be re-checked at the same dose level, unless the patient is very young, has cardiovascular issues or co-morbidities, or if clinical complaints arise.

Pediatric patients must have vitals within the normal range for their age group, and adults with normal established vitals, prior to starting a dose. Dose escalations will take

place as given in the table above. Patient must have no evidence of clinical contraindications with acceptable HR and BP parameters prior to dose escalation occurring. If individuals are found to have a fall in their blood pressure or heart rate outside of normal range, they will have dose de-escalation to the prior tolerated dose level. If they are able to tolerate this lower dose level with normal parameters and no clinical symptomatology they will have a re-challenge of the dose escalation after 2 weeks. If on re-escalation they once again have fall in HR and blood pressure, they will again undergo dose de-escalation to the prior tolerated dose level for 2 weeks and re-evaluated again until the end of the 8-week study. If the patients are already at the lowest doses, they will be given a 2-week rest and re-evaluated after 2 weeks. If HR and BP then fall within normal parameters they will be reintroduced to the study at the lowest study dose of propranolol. If patient is once again found to have fall in HR/BP below normal parameters for age upon an attempt to re-start propranolol, they will be removed from the study. That is, all patients who do not tolerate a dose increase for the 2nd time will be held at the last tolerated dose until the end of the study. If a patient cannot tolerate the lowest doses twice, they will be removed from the study.

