At the 2nd-week re-evaluation, they will be escalated to the new dose (1mg/kg/day) if the baselines HR and BP are WNL. Patients will have HR and BP noted after first new dose (1mg/kg/day) of propranolol to ensure that the propranolol is tolerated. If the HR and BP are WNL, they will continue on this new dose and re-evaluated in 2 weeks for the 4th-week evaluation. If they have a drop in HR and BP to below normal range, they will be de-escalated and remain on the prior dose (0.5mg/kg/day) until the next visit (week 4).

At the 4th and 6th-week evaluation, their baseline vitals will be evaluated and their propranolol escalated to the next dose (if vitals are WNL) and have their HR and BP assessed after first new dose. Propranolol will stay increased or held at old dose depending on HR and BP after the first new dose as described above. If on re-evaluation in 2 weeks a patient continues to have below normal HR and blood pressure on re-challenge of the escalated dose, they will not be escalated and remain at the last tolerated dose for the remainder of the 8 week period with no further re-challenges. For patients with below normal HR and BP and needed their doses held, they will be reported as AEs.

At each study visit, patients will be asked to complete validated questionnaire to assess for tolerance to propranolol treatment, subjective changes in lymphedema symptoms, and self-reported function and activities of daily living (SF-36, LYMPH—ICF, and LYMPH—ICF—LL) (See attached documents, Appendix 2). Physical examination will include weight and BMI, vitals (HR, BP), and measurement of girth of normal and affected extremity.

MRIs and blood tests will be performed at study entry and study endpoint to assess for changes in lymphedema tissue composition[21-23] in response to propranolol.

Blood draws will be performed at study entry, at the midpoint, and study endpoint to assess for changes in circulating biomarkers in response to propranolol treatment.

Correlative biomarkers assessed will include markers of progenitor, endothelial, lymphatic, macrophage, and adipocyte cells, and expression of beta-adrenergic receptors (Table 3).

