## **5.0 TREATMENT PROGRAM**

### **5.1 Overview of Treatment Plan**

Patients will be provided with propranolol prescriptions. Dosing is weight-based (corrected to the closest 10kg increment) and will be prescribed by the PI after medical evaluation by the study cardiologist.

The starting dose of propranolol will be 0.5 mg/kg/day, which is the current institutional dose for initial treatment for cardiovascular and hemangioma indications in children. Dose escalation to 1 mg/kg/day will take place at the 2-week evaluation in the absence of clinical contraindications. If patient tolerates 1 mg/kg/day dose, they will be escalated to 2 mg/kg/day at the 4-week evaluation. In the absence of clinical contraindications, dose escalation will be increased to 3mg/kg/day at week 6 and continued for the duration of the study. A maximum of 8-weeks of therapy may be administered.

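### For a symptomatic fall in heart rate or blood pressure above 0.5 mg/kg/day, the protocol gives incompatible dose instructions and two restart doses, and does not say which governs

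*Combined protocol and SAP*

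**What the plan says.** Several parts of the protocol deal with a fall in heart rate or blood pressure below normal.

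- Section 2.3.2.1: patients whose values fall "outside of normal range, they will have dose de-escalation to the prior tolerated dose level". Symptoms are not part of the trigger. The drug is stopped only at the bottom of the range: "If the patients are already at the lowest doses, they will be given a 2-week rest and re-evaluated after 2 weeks".
- Section 6.1.1.1(c), symptomatic falls: "propranolol will be held for 2 weeks, and re-introduced at the next visit at the lowest tolerated dose".
- Table 5, symptomatic falls: stop the drug and re-evaluate after 2 weeks. If values have recovered, "they will be reintroduced to the study with dose de-escalation to the prior tolerated dose of propranolol".
- Section 5.2.2, falls 2 hours after a new dose: the patient is not escalated and goes home on the current dose. Symptoms are not mentioned.
- Table 1, footnote b: "the patients will remain on their current level of dosage, or decreased to the previous level, or have their medications held". It gives no criterion for choosing among the three.

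On timing, Section 5.1 says "dose escalation will be increased to 3mg/kg/day at week 6 and continued for the duration of the study" and caps treatment at 8 weeks. Table 6 places the only follow-up MRI, QMR, body-water test and skin biopsy at Week 8. On stopping, the Abstract reports that "when patients stopped propranolol or their dose fell below 0.7mg/kg/day, they suffered rebound worsening of their symptoms".

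**The concern.** Staff treating a symptomatic patient on 1, 2 or 3 mg/kg/day cannot both lower the dose and stop the drug. The protocol has no clause giving one section precedence. Two patients with the same event could therefore be managed differently, and both would have been treated according to the protocol. The trial enrols from age 12 and its stated purpose is tolerability, so the instruction for a symptomatic fall should have only one reading.

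Section 6 also disagrees with itself on the restart dose. A patient who has been stopped could be restarted at a level that the sponsor's own experience links with rebound, or at one above it.

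A smaller consequence concerns the response data. For some late falls, the choice of section decides whether the single follow-up assessment is made on a reduced dose or off drug.

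**Working it through.** The plan states no figure to reproduce. The check sets the rules side by side and then works through the calendar.

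**Inputs.** Dose levels start at 0.5 (Week 1), 1 (Week 2), 2 (Week 4) and 3 mg/kg/day (Week 6) (Table 1, Section 5.1). Treatment is capped at 8 weeks (5.1). Visits are at Weeks 1, 2, 4, 6 and 8 (14.2.2). The hold lasts 2 weeks (6.1.1.1(c), Table 5). The rebound threshold is 0.7 mg/kg/day (Abstract). Expected enrolment is 15 to 20 (11.1).

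**Step 1: the rules for a symptomatic fall above 0.5 mg/kg/day.**

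| Section | Trigger as written | Drug | Dose afterwards |
|---|---|---|---|
| 2.3.2.1 | any fall | continues | one level down, re-challenge after 2 weeks |
| 2.4 | fall after the first new dose | continues | previous level |
| 5.2.2 | fall at the 2-hour check | continues | level before the new dose |
| 6.1.1.1(c) | symptomatic fall | stopped 2 weeks | lowest tolerated |
| Table 5 | symptomatic fall | stopped 2 weeks | prior tolerated |

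The first three keep the patient on drug. The last two do not.

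**Step 2: restart dose.** Section 6.1.1.1(d) names 0.5 mg/kg/day as the lowest dose, so that is how lowest tolerated is read here.

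| Fall on (mg/kg/day) | 6.1.1.1(c) | Table 5 |
|---|---|---|
| 1 | 0.5 | 0.5 |
| 2 | 0.5 | 1 |
| 3 | 0.5 | 2 |

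For a fall on 2, 0.5 < 0.7 < 1, so the two restart doses lie on either side of the threshold. The calendar limits where this matters. A hold from 3 starts at Week 6 at the earliest and ends at 6 + 2 = Week 8, when treatment is over. A hold begun on 2 at Week 4 ends at 4 + 2 = Week 6, leaving Weeks 6 to 8 on either 0.5 or 1.

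**Step 3: drug status at Week 8.** A 14-day hold starting at week w ends on day 7w + 14. This is day 56 or later whenever w is 6 or more. Days off drug at the Week 8 assessment are 56 − 7w:

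| Hold starts | Days off drug at Week 8 |
|---|---|
| Week 6 | 56 − 42 = 14 |
| Week 6.5 | 56 − 45.5 = 10.5 |
| Week 7 | 56 − 49 = 7 |
| Week 7.5 | 56 − 52.5 = 3.5 |
| found at the Week 8 visit | 0 |

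Dose at Week 8, Section 2.3.2.1 against Section 6:

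- fall on 3 reported between Weeks 6 and 8: 2 against 0 mg/kg/day;
- fall on 2 found on arrival at Week 6: 1 against 0;
- fall at the Week 6 2-hour check: 2 (also under 5.2.2) against 0, if Section 6 is applied there.

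A hold begun between Weeks 4 and 6 ends between visits. Read strictly, 6.1.1.1(c) then delays restart to the Week 8 visit. The documents do not say whether an extra visit could bring it forward.

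**Step 4: size.** The documents give no rate of symptomatic falls. As an illustration only, suppose k patients are off drug at Week 8 and each has lost the whole effect without going below baseline. The mean response shrinks by k/n. For k = 1 this is 1/20 = 5% to 1/15 = 6.7%; for k = 2 it is 2/20 = 10% to 2/15 = 13.3%. The value of k is an assumption, and the time course of loss after stopping is not given.

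**The case against.** The best defence is that Section 6 is the operative dose-modification section, while 2.3.2.1 is a risk assessment in the background chapter. Section 6 separates symptomatic from asymptomatic falls, and 10.1 refers to Section 6.0 for adverse events requiring removal. A specific safety rule would naturally prevail over a general one. This is a fair reading and probably the intended one. It does not settle everything. No text says so, and 2.3.2.1 is worded as an instruction and makes absence of symptoms a condition for re-challenge, so symptoms were in view. Reading Section 6 as governing also leaves its two restart doses unreconciled and does not say whether it displaces 5.2.2 at the 2-hour check.

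The objection is stronger on the scan. A reader might infer that every symptomatic fall on 3 mg/kg/day is scanned off drug. The documents do not support that. After the Week 6 visit the next scheduled heart rate and blood pressure check is Week 8, and a fall first found then occurs on drug, so a same-day scan is unaffected.

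A reader might also try to estimate the number of patients from Table 7. Its hypotension and bradycardia rates are for asymptomatic events in infants with hemangioma. They say little about symptomatic falls at age 12 or older, and no probability should be built on them.

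Finally, a Week 8 value for every treated patient, whatever the drug status, is a legitimate estimate and agrees with Section 11.5. Scanning held patients early would make follow-up time depend on toxicity, and would place a fasting body-water test and a biopsy soon after a symptomatic event.

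**Conclusion.** The contradiction is in the text and should be corrected. It is mainly a matter of patient safety and consistent dosing: whether a symptomatic patient above 0.5 mg/kg/day is lowered or stopped, and, after a hold from 2 mg/kg/day, whether the restart is at 0.5 or 1 mg/kg/day. The restart comparison assumes that the lowest tolerated dose means 0.5 mg/kg/day, as 6.1.1.1(d) suggests.

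The analytic consequence is secondary. It concerns symptomatic falls found on arrival at Week 6 or reported before Week 8. The number of such patients cannot be derived and is probably small. Only the response outcomes, which are secondary under 11.2.3, are affected. It would be going too far to infer that the trial's main conclusions are at risk: tolerability is recorded throughout, and comparing QMR with the reference methods does not depend on the dose that day.

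**What to change.** 1. State that 6.1.1.1 and Table 5 govern symptomatic falls, including those at the 2-hour check, unless the study cardiologist prefers dose reduction. That choice is medical; the need is for one rule.
2. Use one restart dose in 6.1.1.1(c) and Table 5, for example the prior tolerated level already in Table 5.
3. Amend 2.3.2.1, 2.4, 5.2.2 and Table 1 footnote b to match, saying in each whether symptomatic or asymptomatic falls are meant.
4. Keep the Week 8 assessment time for all patients. Record the actual dose on that day, including 0, and list it beside each response value. If the hold is kept, some patients may still be assessed off drug, but the reader will be able to see which.

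The cost is wording changes and one recorded item per patient. No visit, scan or biopsy is added or moved.

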## 1.0 GOALS AND OBJECTIVES (SCIENTIFIC AIMS)

### 1.1 Primary Aims

- 1.1.1 To assess whether QMR can accurately and quantitatively assess lymphedema severity. QMR results will be compared to validated, gold standard quantitation of total body, extracellular and intracellular water distribution using deuterium (“heavy water”) and sodium bromide (NaBr) and whole body MRI.
- 1.1.2 To assess tolerability, and define and describe the toxicities of propranolol, administered two times daily in patients with lymphedema both by
- 1.1.2a subjective patient-reported symptoms (energy levels, fatigue, dizziness, respiratory issues/wheezing, activities of daily living) by validated questionnaires (SF-36, LYMPH—ICF, LYMPH—ICF--LL)
- 1.1.2b objective measures (heart rate, blood pressure) by physical exam

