**Table 4. Organ Function Criteria**

Hemoglobin	$\geq 8$ mg/dl
Creatinine	Within normal limits ( $<1.2$ )
	OR
Creatinine Clearance	$\geq 60$ mL/min/1.73 m  for patients with creatinine levels above institutional normal

4.1.7.4 **Adequate Cardiac Function Defined as:**

- Baseline heart rate and blood pressure on physical exam within age-defined normal ranges\*
- Normal cardiac rhythm by electrocardiogram
- Normal intracardiac anatomy, pericardial space, and function by echocardiogram (if indicated by screening cardiologist)

\*See Appendix 7.

4.1.7.5 **Adequate Pulmonary Function Defined as:**

- No evidence of dyspnea at rest, no exercise intolerance, and a pulse oximetry  $> 94\%$  if there is clinical indication for determination.

4.1.8 **Pregnancy:** A negative pregnancy test must be obtained in girls who are post-menarchal. Males or females of reproductive potential may not participate unless they have agreed to use an effective contraceptive method.

4.1.9 **Informed Consent:** All patients and/or their parents or legal guardians must sign a written informed consent. Assent, when appropriate, will be obtained according to institutional guidelines.

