**4.2 Exclusion Criteria**

4.2.1 Patients with secondary lymphedema.

4.2.2 Patients who have had surgery or interventional radiology treatment within 4 weeks prior to baseline imaging studies and/or study entry, or those who have not recovered from these interventions.

4.2.3 Patients who are receiving any other investigational agents.

4.2.4 Patients with known contraindications to propranolol therapy, or a history of allergic, hypersensitive, or adverse reaction to propranolol.

- 4.2.5 History of allergic reactions attributed to compounds of similar chemical or biologic composition to propranolol.
- 4.2.6 Patients requiring treatment with drugs known to interact with propranolol including those with other cardiovascular drugs (e.g. antiarrhythmics, calcium channel blockers); migraine drugs; theophylline; neuroleptic, anti-ulcer, and lipid-lowering drugs; and warfarin.
- 4.2.7 Patients must be able to swallow capsules or liquid.
- 4.2.8 Patients who in the opinion of the investigator may not be able to comply with the safety monitoring requirements of the study are not eligible.
- 4.2.9 Uncontrolled intercurrent illness including, but not limited to, ongoing or active infection; asthma, reactive airway disease, or bronchospasm requiring medication; ulcers or nonhealing wounds of the lymphatic malformation; symptomatic congestive heart failure, pericardial effusion, cardiac arrhythmia; or psychiatric illness/social situations that would limit compliance with study requirements.
- 4.2.10 Other contraindications including pheochromocytoma, bradycardia, first degree heart block, decompensated heart failure.

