#### 9.1.1 Structure

Propranolol hydrochloride (2-Propanol, 1-[(1-methylethyl)amino]-3-(1-naphthalenyl)-, hydrochloride is a synthetic, nonselective antagonist of beta-adrenergic receptors. It has been used extensively in pediatrics for more than 40 years, principally for cardiac indications (e.g. supraventricular tachycardias) but more recently for other indications. In particular, broad experience with propranolol for the treatment of pediatric hemangiomas has recently emerged, after the initial serendipitous observation of its efficacy in this condition[30].

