## **10.0 CRITERIA FOR REMOVAL FROM PROTOCOL THERAPY AND OFF STUDY CRITERIA**

10.1 **Criteria for Removal from Protocol Therapy**

- Intercurrent illness that prevents further administration of treatment.
- Adverse Events requiring removal from study (See Section 6.0).
- Refusal of further protocol therapy by patient/parent/guardian

- d) Non-compliance that in the opinion of the investigator does not allow for ongoing participation.
- e) Completion of 2 months of therapy.
- f) Physician determines it is not in the patient's best interest.

Patients who are off protocol therapy are to be followed until they meet the criteria for Off Study (see below). Ongoing adverse events, or adverse events that emerge after the patient is removed from protocol therapy, but within 30 days of the last dose of investigational agent, must be followed until resolution or stabilization of the adverse event. Follow-up data will be required unless consent is withdrawn.

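### Table 5 gives two actions for a transient bronchospasm during a URI, and implies restarting propranolol after URI-associated bronchospasm that needed treatment

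*Combined protocol and SAP*

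**What the plan says.** The bronchospasm part of Table 5 (Section 6.1) has three rows:

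- **Row 1**, a transient or self-limited episode: "Clinical evaluation, may continue at same dose".
- **Row 2**, an episode associated with a URI: "Hold propranolol till URI resolves; if >7 days, off protocol".
- **Row 3**, "Not associated with URI, persistent or requiring new medical treatment": discontinue, off protocol therapy.

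Other sections touch on the same event. Section 2.3.2.4 says only that respiratory symptoms will be monitored. The illness paragraph in 2.3.2.3, which names URIs, holds the dose until the patient tolerates oral intake and does not mention Table 5. Exclusion 4.2.9 lists, under uncontrolled intercurrent illness, "asthma, reactive airway disease, or bronchospasm requiring medication". Section 9.1.1 states that propranolol "is a synthetic, nonselective antagonist of beta-adrenergic receptors". Primary aim 1.1.2a covers patient-reported "energy levels, fatigue, dizziness, respiratory issues/wheezing, activities of daily living". Section 10.1 refers removal for adverse events back to Section 6.0 and separately lets the physician stop therapy in the patient's interest. The stopping rules in 14.2.3 deal only with failed initiation or failed escalation.

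**The concern.** There are two defects, both in the table's own wording.

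First, row 1 does not mention URI and row 2 does not mention duration. A brief wheeze during a cold satisfies both. One row lets the patient continue and the other tells the investigator to hold.

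Second, row 2 does not depend on whether the bronchospasm needed treatment, and its hold is tied to the infection alone. If the URI clears within 7 days, the row implies that propranolol resumes, even if the patient needed new medication for bronchospasm and even if the airway has not fully settled. Row 3 takes a patient with the same treated episode and no URI off therapy.

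What is at stake is mainly patient safety: re-exposure to a nonselective beta-blocker after treated bronchospasm, with no stated check at restart. A smaller point concerns the tolerability data. The row applied decides whether the patient is recorded as having stopped for intolerance, in a trial whose primary endpoint is tolerability and whose primary aim names wheezing.

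**Working it through.** The plan gives no figure on this point, so the main check sets the rows against every type of episode.

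**Step 1. The two readings of row 3.** Narrow reading: not URI-associated, and either persistent or needing new treatment. Broad reading: any one of three alternatives, namely not URI-associated, persistent, or needing new treatment. The punctuation allows both.

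**Step 2. Rows that apply to each episode** (taking transient or self-limited to mean that no new treatment was needed):

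| Episode | Narrow reading | Broad reading |
|---|---|---|
| URI, transient, untreated | rows 1 and 2 | rows 1 and 2 |
| URI, persistent, untreated | row 2 | rows 2 and 3 |
| URI, treated | row 2 | rows 2 and 3 |
| No URI, transient, untreated | row 1 | rows 1 and 3 |
| No URI, persistent, untreated | row 3 | row 3 |
| No URI, treated | row 3 | row 3 |

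On the narrow reading 1 of 6 episodes has two actions; on the broad reading 4 of 6 do. The first line conflicts on either reading. On the narrow reading the treated URI episode falls in row 2 alone, which implies a restart. No episode falls in all three rows.

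**Step 3. Whether another section settles it.**

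- Section 10.1 returns the reader to Section 6.0, so Table 5 is the operative rule.
- Section 14.2.3 does not cover bronchospasm.
- The hold in 2.3.2.3 ends at a different point (oral intake) and sets no respiratory condition.
- The 2-hour check in 5.2.2 follows an escalated dose, not a restart.
- Study visits are at weeks 1, 2, 4, 6 and 8 (14.2.2). From week 2 they are 14 days apart, so a hold of up to 7 days and the restart can both fall between visits. Table 6 does show adverse event evaluation every week, but vital signs and physical examination only at the visits.

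**Step 4. Scale.** Inputs: 1.9% for bronchopulmonary symptoms (Table 7, infantile hemangioma) and 15 to 20 patients (11.1). Applying the infant rate here is an assumption.

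- Expected events: 15 × 0.019 = 0.285; 20 × 0.019 = 0.38.
- Chance of at least one: 1 − 0.981^15 = 0.250; 1 − 0.981^20 = 0.319.

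The documents do not give the share associated with a URI. At an assumed 10% to 50%, the chance of at least one URI-associated event runs from 1 − (1 − 0.0019)^15 = 0.028 to 1 − (1 − 0.0095)^20 = 0.174. Those that also need new treatment and clear within 7 days are a subset of these, and the documents do not allow them to be quantified.

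**The case against.** Much can be said for the plan. Treating bronchospasm during a URI differently is a defensible clinical choice, because the infection is an alternative cause and the protocol's causality guidance recognises such explanations. The hold is capped at 7 days. The table is labelled as guidelines, row 1 is permissive while row 2 is specific, and 2.3.2.3 also favours holding during illness. The physician may stop therapy at any time, and the Study Chair must be told of any dose modification. Hold ordinarily means pausing and resuming the same prescription, so the lack of a restart dose carries little weight by itself.

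These safeguards permit a safe choice but do not say which row applies or make restart depend on the airway. A sensible investigator would probably hold in the overlapping case; the table should say so.

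Three stronger inferences are tempting, and the documents do not support them:

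- *That row 3 and exclusion 4.2.9 already bar restart after treated bronchospasm.* Row 3 opens by excluding URI episodes and reaches them only on the broad reading. Exclusion 4.2.9 decides who may enrol and does not govern an enrolled patient. It shows only an inconsistent safety intent: a condition listed among the reasons for refusing entry does not clearly prevent re-exposure.
- *That most of the table contradicts itself.* This needs the broad reading, under which every non-URI episode would be discontinued and row 1 would have no independent effect for such patients. That makes it the less natural reading.
- *That one event can mean continue, hold or discontinue.* As the grid shows, no episode meets more than two rows.

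**Conclusion.** The point holds in a limited form. On any reading, Table 5 gives a transient URI-associated episode two different actions. On the more natural reading of row 3, it also implies restarting propranolol after URI-associated bronchospasm that needed new treatment, with the hold ending on resolution of the URI alone. Row 3 is ambiguous about whether it reaches URI episodes, and no other section resolves this.

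The practical size is small: 0.29 to 0.38 bronchopulmonary events of any kind expected in 15 to 20 patients, a 25% to 32% chance of at least one, if the infant rate applied to patients aged 12 or over. That transfer is uncertain, not least because 4.2.9 excludes uncontrolled reactive airway disease. A reader might infer that the toxicity or efficacy results are at risk. They are not to any material degree: the adverse event is counted whichever row is used, and the effect on efficacy results is negligible. The case for change is patient safety, and it is enough because the correction is cheap.

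**What to change.** Reword the three bronchospasm rows of Table 5:

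- **Row 1.** Not associated with URI, transient, no new medical treatment: clinical evaluation, dose may stay the same.
- **Row 2.** Associated with URI, no new medical treatment: hold until both the URI and the bronchospasm have resolved; if this takes more than 7 days, off protocol therapy. Restart in clinic at no more than the pre-hold dose, with respiratory symptoms, heart rate and blood pressure checked 2 hours after the first dose, and pulse oximetry if clinically indicated, as in 4.1.7.5.
- **Row 3.** New medical treatment required, with or without URI; or persistent and not associated with URI: discontinue, off protocol therapy.

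The six episodes in the grid, in order, then fall in rows 2, 2, 3, 1, 3 and 3, one action each.

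In 2.3.2.3, add one sentence stating that Table 5 applies if bronchospasm is present. A general instruction to resume the full dose after any illness hold should not be added there, because it would allow an unchecked restart after a long interruption.

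The cost is the rewording, an occasional extra clinic visit (at most 0.38 expected in 20 patients at the 1.9% rate, even if every such event were URI-associated and restarted), and possibly one more discontinuation. Sample size, dose levels and the visit schedule are unchanged.
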